### 7.2. Regulatory action

In the frame of 13th PSUR assessment, data submitted raised concern regarding cardiovascular safety beyond the already recognized risk for venous thromboembolism. Analysis of pooled data from randomized studies in around 7,500 post-menopausal women with osteoporosis showed an increased risk of myocardial infarction with Protelos/Osseor as compared with placebo (1.7% versus 1.1 %), with a relative risk of 1.6 (95% CI, 1.07 to 2.38), and an increased risk of venous thrombotic and embolic events — 1.9% versus 1.3 % with a relative risk of 1.5 (95% CI, 1.04 to 2.19).

As a result of this assessment, an increased risk for serious cardiac disorders, including myocardial infarction has been identified and risk minimization measures specifically targeting this identified risk were recommended by the CHMP. These risk minimization measures included a restriction of the target population by excluding patients with established, current or past history of ischaemic heart disease, peripheral arterial disease and/or cerebrovascular disease and/or uncontrolled hypertension, and restricting the indication to severe osteoporosis in postmenopausal women at high risk for fracture to reduce the risk of vertebral and hip fractures and the treatment of severe osteoporosis in adult men at increased risk of fracture. Patients with significant risk factors for cardiovascular events (e.g. hypertension, hyperlipidaemia, diabetes mellitus and smoking) should only be treated with strontium ranelate after careful consideration. In addition, strontium ranelate therapy should only be initiated by a physician with experience in the treatment of osteoporosis. These changes were disseminated in the form of a DHPC in May 2013.

In view of this newly identified risk of serious cardiac disorders, an overall benefit/risk review under Article 20 of regulation (EC) No 726/2004 started in May 2013 and was finalized on 20 February 2014 ([EMA/112925/2014, 2014](#)). This led to a restriction of the indication to patients (postmenopausal women and men) with severe osteoporosis at high risk of fracture for whom treatment with other medicinal products approved for the treatment of osteoporosis is not possible due to, for example, contraindications or intolerance. As part of RMM, a new DHPC was disseminated in March 2014.

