### 9.3. Variables

#### 9.3.1. Safety endpoints

**Ascertainment of cases:** cases will be all persons with a first occurrence after cohort entry of:

- Acute myocardial infarction.
- Thromboembolic events (deep venous thrombosis and pulmonary embolism).
- Cardiovascular death.

Cases will be identified from the medical records (see codes in Appendix 14.3).

Acute myocardial infarction has been recently validated in all of the participating data sources (Coloma, 2013; Ramos, 2012) and will therefore not need further linkage or validation studies.

Thromboembolic events have been validated in the UK CPRD/THIN (Lawrenson, 2000) and Aarhus (Severinsen, 2010), and these previously validated algorithms will be used to identify cases. A random sample of cases of thromboembolic events in each data source will be validated using either free text manual review (IPCI, HSD, and Aarhus) or linkage to hospital admissions data (THIN and SIDIAP). If the estimated positive predictive value in these samples is >75%, no further validation will be performed for thromboembolic events. Otherwise, all the events observed in the safety study (i.e. cases) will be individually validated, and only those found to be valid (either by manual review or related hospital admission from hospital records databases, as proposed above) will be defined as cases.

As for cardiovascular death, HSD, IPCI and SIDIAP will combine ICPC and ICD9/ICD10 codes (for hospital admission/primary care records) respectively with mortality using a time specific window to define cardiovascular death. In THIN, data will be linked to the official mortality registry (office for national statistics) for cause of death. In Aarhus, safety endpoints will be identified in the patient registry (hospital discharge and death registry) and no manual validation in the medical records will be done.

**Control selection:** In the nested case control study, each case will be matched by age (same year of birth), index date, gender, and country/data source to 10 controls selected from the cohort using incidence density sampling.

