### 9.5.2. Safety study

Bearing in mind that the number of incident users identified in 2012 is of 5,819 patients, we expect that at least 30,000 incident SR users will be included for the period 2004-2012, and a lower number of people (500 to 1,000 per annum) will be eligible for the prospective cohort of incident users as identified in 2013-2015 due to the DHPC, making a total of 31,500 to 33,000 SR users. With the combined prevalence of exclusion criteria described above (29.5% for men and 19.2% for women) (Abrahamsen, 2014) and a 90% participants being of female gender (based on feasibility counts for 2012 in Table (9.5) 1), a minimum of 25,128 incident SR users would be included. Considering a prevalence of SR use of 20% in osteoporotic treated population, around 125,640 incident bisphosphonate users are expected, making a total of over 150,000 study participants.

We assume a conservative annual incidence rate of acute myocardial infarction of 0.19/100 person-years in the general population of participants in EU-ADR databases (Coloma, 2013). Based on this and assuming an average follow-up period after cohort entry of 2 years we would expect 570 cases. Accepting an alpha risk of 0.05, with 90% power, and a prevalence of SR use of 20% amongst controls, **415** MI cases and a 1:10 case-control ratio (**4150** controls) would suffice to recognize as statistically significant an odds ratio greater than or equal to 1.5. Different scenarios of SR use ranging from 10% to 40% and the corresponding number of MI cases required for an  $OR \geq 1.5$  (at fixed alpha 0.05, power 90%) are shown in Figure (9.5.2) 1.

[figure not shown]
**Figure (9.5.2) 1 - Number of MI cases required to ensure 90% power to detect as significant an  $OR \geq 1.5$  for the association between SR use and MI.**

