## Information bias

Information bias may occur to not measuring correctly exposure, outcomes or co-variables.

Regarding exposure, most databases that participate in the study capture prescriptions rather than dispensings. Misclassification of exposure may occur due to lack of ‘picking up’ the prescribed medication and non-compliance. This may overestimate utilization of SR/BP and lead to non-differential misclassification of the comparative studies. Misspecification of the risk window may lead to information bias. The effect of a potential misspecification will be addressed in sensitivity analyses

Lack of recording of certain co-variables (e.g. history of fractures rather than BMD) may lead to misclassification and underestimation of the contra-indications and new indications. Similarly, lack of recording of safety events may lead to misclassification of the safety endpoints. However, previous work has shown very high validity of the coding of myocardial infarction, with positive predictive values ranging from 75% to 100% within EU-ADR Alliance partners (Coloma, 2013). DVT and VTE were only validated in some databases before and will therefore need validation in each of the data sources. Cardiovascular death may be misclassified if no autopsy is done. Validation studies will be conducted in databases where this information is not yet available (See Section 9.3.1).

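### The VTE validation gate in section 9.3.1 rests on one overall PPV, so it cannot detect a PPV that differs between strontium ranelate and bisphosphonate users

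*Protocol*

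**What the plan says.** Section 9.3.1 sets the rule for VTE: "A random sample of cases of thromboembolic events in each data source will be validated using either free text manual review" (IPCI, HSD, Aarhus) or linkage to hospital admissions (THIN, SIDIAP). Then: "If the estimated positive predictive value in these samples is >75%, no further validation will be performed for thromboembolic events". If the threshold is not exceeded, "all the events observed in the safety study (i.e. cases) will be individually validated", and only confirmed events count as cases. The Information bias part of section 9.9 explains the need: "DVT and VTE were only validated in some databases before and will therefore need validation in each of the data sources".

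The rule contains no comparison by drug. It does not say whether the PPV is judged within each database or over all samples together. It says nothing on hiding the drug from free-text reviewers.

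Section 7.2 describes the cardiac concern as going "beyond the already recognized risk for venous thromboembolism", and gives a VTE relative risk of 1.5 (95% CI 1.04 to 2.19) against placebo from pooled randomized data.

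Section 9.3.1 is also inconsistent on Aarhus. It lists Aarhus for free-text review of VTE, yet two paragraphs later says that Aarhus endpoints come from registries with no manual check of the records.

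**The concern.** Comparing thromboembolic risk between SR and BP is a primary safety objective (section 8). For that comparison, the overall share of false-positive VTE codes matters less than whether the share is the same on both drugs. If there is no true effect and the PPV is equal, false positives cancel out of the odds ratio. If the PPV differs, they do not.

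A difference is plausible. Clinicians knew of the VTE risk with SR, and section 9.3.2 lists a VTE history among the contraindications, so suspected VTE may be recorded at a different threshold in SR users. Most cases in any sample will be BP users, so they dominate an overall PPV, and the gate can be passed whatever the SR value is within a wide range.

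No other part of the protocol covers this. The sensitivity analyses in section 9.7.5 vary the gap period and the risk window and exclude Spain. Section 9.9 treats endpoint misclassification only in general terms, and its statement on non-differential error concerns exposure.

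**Working it through.** **The plan's own figures.** The protocol gives no VTE case count, validation sample size or PPV by drug, so there is no VTE figure to reproduce. The 415 cases in section 9.5.2 concern myocardial infarction and are not used here. The cohort sizes in that section do reproduce: 31,500 × (1 − (0.9 × 0.192 + 0.1 × 0.295)) = 31,500 × 0.7977 ≈ 25,128 SR users, and 25,128 / 0.20 = 125,640 BP users.

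**Inputs.**
- Gate: PPV above 75% (section 9.3.1).
- Contrast: current SR against current BP by conditional logistic regression (section 9.7.3.3).
- SR share: section 9.5.2 assumes "a prevalence of SR use of 20% amongst controls". The cohort counts give 25,128 / 150,768 = 16.7%.
- PPV gap between drugs: an assumption, shown at 5, 10 and 15 points.

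**Step 1, the bias factor.** Of n_SR and n_BP coded cases, n_SR × PPV_SR and n_BP × PPV_BP are true. The controls are unaffected. If coding captures the same fraction of true events on both drugs,

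observed OR = true OR × PPV_BP / PPV_SR.

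**Step 2, what passes.** Let s be the SR share of coded cases and d = PPV_BP − PPV_SR. Then PPV_BP = overall PPV + s × d, and PPV_SR = PPV_BP − d. With an overall PPV of 80% (gate passed) and s = 0.20:

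| d (points) | PPV_SR | PPV_BP | Factor |
|---|---|---|---|
| 5 | 76% | 81% | 1.07 |
| 10 | 72% | 82% | 1.14 |
| 15 | 68% | 83% | 1.22 |
| −5 | 84% | 79% | 0.94 |
| −10 | 88% | 78% | 0.89 |
| −15 | 92% | 77% | 0.84 |

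**Step 3, sensitivity to the SR share.** With s = 16.7%, gaps of 5, 10 and 15 points again give 1.07, 1.14 and 1.22. If 20% is the share among controls, as section 9.5.2 words it, the 68%/83% case has an SR share among coded cases of 0.2 × 1.22 / (0.8 + 0.2 × 1.22) = 23.4%. The overall PPV is then 0.234 × 68% + 0.766 × 83% = 79.5%, and the gate is still passed.

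**Step 4, how far the gate can be stretched.** Take PPV 60% on SR and 90% on BP, a true OR of 1.0 and 20% SR use in controls. The observed OR is 0.90 / 0.60 = 1.50. The SR share of coded cases is 0.30 / 1.10 = 27.3%, and the overall PPV is 0.273 × 60% + 0.727 × 90% = 81.8%. The gate is passed. This is a stress case, not an expectation.

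**Step 5, bias toward the null.** Suppose false positives arise at the same rate on both drugs and make up 20% of coded cases, with a true OR of 1.5.
- SR share of true cases: 0.30 / 1.10 = 27.3%.
- SR share of coded cases: 0.8 × 27.3% + 0.2 × 20% = 25.8%.
- PPV: 84.5% on SR and 78.4% on BP.
- Observed OR: 1.5 × 78.4 / 84.5 = 1.39.

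The overall PPV is 80%, so the gate is passed here too, and a real effect is diluted.

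**The case against.** **No evidence of over-coding.** A reader might infer that VTE is over-coded in SR users and that the SR odds ratio will be inflated. The documents do not support that. They report no PPV by drug, and a recognised risk may just as well lead to more true VTE being found. Step 5 shows that bias toward the null can pass the same gate. What stands is that the gate cannot tell these situations apart.

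**Where the sample comes from.** A reader might infer that the sample is drawn from whole databases, where SR users are rare. Section 9.3.1 defines cases as first events after cohort entry, which favours the SR/BP cohort. The concern does not need the other reading, though the protocol should say so explicitly.

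**Matters for the SAP.** Masking and strata are not mentioned, which is not a decision against them, and section 9.7 defers detail to an SAP. That is fair for those two items. The stopping rule, however, is fixed in the protocol and ends validation once it is passed. Masking also has limited reach: THIN and SIDIAP use linkage and hold 514 + 4,008 = 4,522 of the 5,819 incident SR users of 2012 (78%).

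**Size.** The PPV gaps are assumed, and a 5-point gap moves the odds ratio by only about 7%. A false-positive rate for the VTE test cannot be derived, because the protocol gives no VTE case count.

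**Conclusion.** The point holds as an inexpensive improvement, not as a demonstrated bias. As written, the gate cannot detect a PPV that differs between SR and BP users, whether it is applied by database or over all samples. If there is a difference, the odds ratio is off by PPV_BP/PPV_SR: about 1.07, 1.14 or 1.22 for gaps of 5, 10 or 15 points with the SR PPV lower, and 0.94, 0.89 or 0.84 with it higher. These factors assume an overall PPV of 80%, an SR share near 20% and equal capture of true events on both drugs. The gaps are assumptions, and the documents do not establish their existence or direction.

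The two statements on Aarhus conflict as they stand. The second may be meant for cardiovascular death only, since it sits in that paragraph, but it speaks of safety endpoints in general.

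**What to change.** In section 9.3.1:
- State that the validation sample is drawn from coded VTE cases in the SR/BP safety cohort, stratified by exposure at the event, with SR over-sampled.
- Mask drug exposure in the free-text review.
- Report PPV with a 95% CI by drug. Pool the SR PPV across databases where SR cases are few, as is likely in IPCI and Aarhus (42 and 46 incident SR users in 2012).
- Even when the 75% gate is passed, report a sensitivity odds ratio: observed OR × PPV_SR / PPV_BP, carrying the uncertainty of both PPVs.
- Reconcile the statements on manual validation in Aarhus.

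A fixed cut-off on the PPV difference is not advisable. With equal true PPVs of 80%, an observed gap above 10 points arises by chance 37% of the time with 25 cases per drug and 17% with 50. A 75% rule for each drug in each database would not be workable in the small sources.

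The cost is modest: wording, redaction of drug names, and a stratified draw. The SR PPV will be imprecise where cases are few. At a PPV of 80%, the 95% half-width is 1.96 × √(0.8 × 0.2 / n), or about 16 points for n = 25, 11 for n = 50 and 8 for n = 100. This is why the SR estimate should be pooled and its uncertainty carried into the corrected odds ratio.

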#### 9.2.6.2. Safety study

Patients will be followed from the date of incident prescription of strontium ranelate or oral bisphosphonate (after one year of non-use) which follows the latest of the following dates:

- Start of study period.
- One year of valid data in database.

Until the earliest date of:

- The end of enrolment in the database (due to moving out or death).
- Date of last data capturing in the database.

The safety study will be performed in two periods (up till May 2013 and from June 2013 onwards) based on the date of cohort entry.

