##### *General potential confounders*

- Age (matching factor).
- Gender (matching factor).
- Calendar time (matching factor).
- Alcohol abuse (if available).
- Health seeking behaviour: number of visits to general practitioner or hospital contacts in the year before cohort entry/index date.
- Use of any drugs: number of different compounds used in the year previous to cohort entry/index date.

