### 9.7.1. Statistical elements

Categorical data will be presented in counts (n) and proportions (%) with 95% confidence intervals (95% CIs). 95% CIs will be calculated using the normal or Poisson distribution.

For continuous data, number of observations (n), number of patients with missing information (if applicable), mean, and standard deviation will be reported for normally distributed variables. Median and inter-quartile range will be presented for non-normally distributed continuous variables.

For the comparison of groups Chi-square, independent samples T-tests and Wilcoxon tests will be used to test for differences in categorical, normally distributed and non-normally distributed continuous variables respectively.

Analyses will be performed for the overall eligible population but also after stratification by gender, period, and presence/absence of (contra) indications, when applicable/relevant.

Effectiveness of RMM will be assessed using interrupted time series analyses.

Nested case-control analyses will be done using conditional logistic regression.

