### 9.7.3.3. Relative risks

Using a matched case control approach we will use conditional logistic regression to estimate the association with the occurrence of endpoints and between current use of SR and 1) past use of study drugs; 2) current use of bisphosphonates. Control for confounding will be based on the change in estimate method as proposed by Greenland *et al* (1993). All analyses will be stratified by period. We will primarily consider factors measured at baseline, and only for those at index date for which we are sure they cannot be an intermediate between drug exposure and outcome.

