## Confounding

Due to the observational design chosen, causality in the observed associations will not be established. Instead, associations between drug use and risks will be assessed. As confounding by indication (with SR patients most likely to suffer more severe osteoporosis) will likely produce differences between SR and bisphosphonate users, especially after the different DHPCs, we will use several methods to deal with between-person confounding:

1. Restriction: comparative studies will be conducted only in persons without contra-indications to restrict the population to those that would be prescribed SR according to the new label.
2. Matching: for the comparative studies we will match cases to controls on age, sex, date, country.
3. Adjustments: we will adjust for all co-variables that are associated with a 10% change in the primary risk estimate.

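### Controls are matched on index date but not on cohort-entry period, although the relative-risk analyses are stratified by entry period; restrict control sampling to the case's entry period

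*Protocol*

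**What the plan says.** Section 9.3.1 states that "each case will be matched by age (same year of birth), index date, gender, and country/data source to 10 controls", and that these controls are "selected from the cohort using incidence density sampling". The abstract gives the same matching factors. Section 9.9 repeats them in short form: "for the comparative studies we will match cases to controls on age, sex, date, country". None of the three places lists cohort-entry date or period. Section 9.3.4 names calendar time as a matching factor, but in section 9.3.1 that is the index date.

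The periods are defined differently. Section 9.2.6.2: "The safety study will be performed in two periods (up till May 2013 and from June 2013 onwards) based on the date of cohort entry". Follow-up in the same section ends only at end of enrolment or last data capture, not when treatment stops and not in May 2013.

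Section 9.7.3.3, on conditional logistic regression, adds: "All analyses will be stratified by period". An unstratified analysis is planned as well; section 9.7.1 says "Analyses will be performed for the overall eligible population but also after stratification by gender, period".

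**The concern.** Matching uses one date (the event) and stratification uses another (cohort entry). Since follow-up continues past June 2013, every risk set after that date holds people from both entry periods. A case who entered from June 2013 can therefore be given controls who entered years before, and the protocol does not say what happens to such a mixed set.

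The comparison from June 2013 onward is a stated objective in section 8 and is the thinner of the two strata. If out-of-period controls are discarded, it does not get the planned ten controls per case. If they are kept and their entry period is ignored, late-entry cases are compared with controls who started treatment when strontium ranelate was used far more. In a safety study, the resulting error would tend towards false reassurance.

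**Working it through.** **The plan's own figure.** Section 9.5.2 gives 415 MI cases at 1:10 for an odds ratio of 1.5, 90% power, alpha 0.05 and 20% exposure in controls. Exposure in cases is 0.2 × 1.5 / (1 + 0.2 × 0.5) = 0.2727. The unpooled two-sided formula gives (1.960 + 1.282)² × (0.2727 × 0.7273 + 0.2 × 0.8 / 10) / 0.0727² = 426, within 3% of 415. The protocol gives no figure by period.

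**Share of controls from the other period.** Let t be years since 1 June 2013.
- Earlier entrants still at risk: ∫ S(u) du from t to t + 9.42. Entry is assumed constant from January 2004 to May 2013, 9.42 years.
- Later entrants at risk: r × ∫ S(u) du from 0 to t.
- Out-of-period share = earlier / (earlier + later), averaged over t with weight proportional to the later entrants at risk (constant event rate).

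Inputs:
- S(u) = exp(−u/m). m = 2 years is the planning follow-up in section 9.5.2; m = 5.5 years is the THIN average in section 9.4.3; no loss is the extreme.
- r = 1 or 0.5 (total entry unchanged or halved). This is an assumption, because the protocol gives no bisphosphonate inflow after 2013.
- Data end December 2014, 2015 or 2016, following the three extraction waves in section 6.

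Out-of-period controls for cases who entered from June 2013:

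| Mean follow-up | Entry after June 2013 | to Dec 2014 | to Dec 2015 | to Dec 2016 |
|---|---|---|---|---|
| 2 years | unchanged | 61% | 46% | 36% |
| 2 years | halved | 75% | 62% | 51% |
| 5.5 years | unchanged | 80% | 70% | 62% |
| 5.5 years | halved | 89% | 82% | 76% |
| no loss | unchanged | 90% | 85% | 80% |
| no loss | halved | 95% | 92% | 89% |

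The share exceeds one half in 16 of the 18 scenarios. Both exceptions use the 2-year follow-up with unchanged entry.

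**If those controls are dropped.** Between 6.4 and 0.5 of the 10 controls remain, and 1% to 59% of sets have none. Taking information per set as M/(M+1) relative to 10/11, and averaging over the binomial number of controls left, 92% down to 25% of the planned information remains. For scale, the pooled two-proportion formula with the plan's inputs needs 385 cases at ten controls, 422 at five, 532 at two and 716 at one.

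**If they are kept by the case's period and their entry period is ignored.** Section 9.5.2 expects at least 30,000 new strontium ranelate users in 2004–2012, or 30,000 / 9 = 3,333 a year, then 500 to 1,000 a year. Its bisphosphonate count is five times the strontium ranelate count (125,640 / 25,128), so the earlier odds are 0.20. Assume bisphosphonate inflow unchanged at 5 × 3,333 = 16,667 a year, 750 later strontium ranelate starters a year, and equal persistence on both drugs. The later odds are then 750 / 16,667 = 0.045. The strontium ranelate fractions are 0.1667 and 0.0431. With a true odds ratio of 1:
- 36% out-of-period: controls 0.36 × 0.1667 + 0.64 × 0.0431 = 0.0876, odds 0.096; observed 0.045 / 0.096 = 0.47.
- 90% out-of-period: controls 0.90 × 0.1667 + 0.10 × 0.0431 = 0.1543, odds 0.1825; observed 0.045 / 0.1825 = 0.25.

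This illustrates direction and is not a forecast. If earlier strontium ranelate users stopped disproportionately after the 2013 communication, the bias shrinks. It concerns the contrast with current bisphosphonate use. Against past use, earlier entrants have had longer to stop, which pulls the other way, so no direction is claimed there.

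**Who is not affected.** Risk sets before June 2013 contain only earlier entrants. For earlier entrants with events after June 2013, only 4% to 42% of controls come from the other period under the same scenarios.

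**The case against.** The best defence is section 9.2.6.2 itself. If the safety study is performed in two periods by entry date, the cohort in section 9.3.1 may mean that period's cohort, and controls then come from within it. Section 9.5.2 also speaks of the later entrants as a cohort of their own, and details of risk-set construction often sit in the analysis plan. That reading is available and would remove the problem. However, the sampling rule itself refers only to the cohort, and the three matching lists all omit entry period, so the literal text yields mixed sets.

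A reader might infer that most controls of late-entry cases fall in the wrong stratum. The documents do not establish that. With the 2-year follow-up and unchanged entry, the in-period share at time t is (1 − e^(−t/2)) / (1 − e^(−(t+9.42)/2)): 40% at one year, 63% at two and 83% at 3.5. A majority needs longer follow-up, lower inflow or an early data cut.

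Nor do sets have to break up or the estimate have to be biased. Dropping out-of-period controls leaves a valid density sample. Fitting entry period and its interaction with exposure in the conditional model keeps whole sets. Bias needs one particular handling, which the protocol does not prescribe.

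Finally, the late stratum is thin in any case. Section 9.5.2 implies 1,500 to 3,000 later strontium ranelate starters, about 79.8% eligible (25,128 / 31,500). Over 2 years at 0.19 per 100 person-years, that gives 1,500 × 0.798 × 2 × 0.0019 = 4.5 to 9.1 MI cases at the background rate. More controls will not make that estimate precise. This limits the value of the fix but does not remove the need to avoid a mixed comparison.

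**Conclusion.** The point holds as a mismatch between the sampling rule and the stratification. For cases who entered from June 2013, a material share of controls, roughly 36% to 95%, would have entered earlier. The range rests on assumed constant entry, exponential or no loss, and an assumed inflow after 2013. The consequence is either lost precision with a valid estimate, or an odds ratio against bisphosphonates that is probably too low, depending on handling that the protocol leaves open.

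The wording on stratifying all analyses might suggest that every safety result is affected. It is not: the overall-population analysis in sections 8 and 9.7.1 does not depend on the entry-period split, and cases with events before June 2013 have single-period risk sets. The 415-case calculation is not altered. This is a cheap improvement, not a fault that invalidates the design.

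**What to change.** In the abstract, section 9.3.1 and section 9.9, add cohort-entry period (up to May 2013, or from June 2013) to the matching factors. Equivalently, state in section 9.3.1 that risk sets are formed separately within each entry-period cohort. Either wording removes all out-of-period controls and keeps the 1:10 ratio wherever enough controls exist. The cost is one more variable in the common sampling script, and a few late-entry cases may find fewer than ten controls.
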